2.1 Study Overview

This is a Phase 2b, randomized, double-blind, placebo-controlled, parallel-arm, multicenter study to evaluate the efficacy and safety of two SC treatment regimens of tralokinumab in adult subjects with uncontrolled, severe asthma requiring high-dose ICS and LABA with or without additional controller medications (high-dose ICS defined as a total daily dose $> 500 \mu g$ fluticasone DPI or $> 440 \mu g$ MDI; GINA, 2009; National Heart, Lung, and Blood Institute, 2007). Approximately 100 sites around the world will participate in the study. A total of approximately 390 subjects will be randomized in a 1:1 ratio to one of 2 cohorts (Cohort 1 or Cohort 2). Within each cohort, subjects will be randomized in a 2:1 ratio to receive tralokinumab (300 mg) or placebo as follows:

Cohort 1: Tralokinumab 300 mg (n = 130) or Placebo (n = 65) as 2 SC injections Q2W for 50 weeks for a total of 26 doses

Cohort 2: Tralokinumab 300 mg (n = 130) or Placebo (n = 65) as 2 SC injections Q2W for 12 weeks followed by Q4W for 38 weeks for a total of 16 doses

Subjects will be stratified at screening by the number of asthma exacerbations in the past 12 months (2 versus > 2 but \leq 6 exacerbations) and by chronic OCS use (presence versus absence). To maximize the probability of obtaining treatment balance within Japanese population for the purpose of PMDA filing, the Japanese will be randomized separately.

A 5-week screening/run-in period (Week -5 to -1 [Day -1) will precede investigational product administration. Starting at Week -4 (Day -28), subjects will receive a fixed-dose combination product of fluticasone/salmeterol, either as an MDI (230 μ g/21 μ g) at a dose of 2 inhalations twice per day or as a DPI (500 μ g/50 μ g) at a dose of one inhalation twice per day. Sites/subjects will be permitted to use either presentation of fluticasone/salmeterol if approved and available for use in their country. If the subject is also taking additional asthma controller medications (including leukotriene modifiers, theophylline, chromones, or OCS \leq 20 mg/day), then these medications should be continued at a stable dose during the screening/run-in period. During the study, subjects may use inhaled reliever therapy (e.g., SABA or short-acting anticholinergic) on an as-required basis as documented in their Personalized Asthma Action Plan.

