Subjects will continue to receive the same fixed-dose combination product of fluticasone/salmeterol with or without additional asthma controller medications at a stable dose during the treatment period and through Week 53. Subjects who experience an asthma

Version 2.0

exacerbation during the treatment period will be treated accordingly and will remain in the study.

Subjects will return to the clinic at Week 53 for an assessment of the efficacy endpoints. Subjects will have 3 additional follow-up visits at Weeks 59, 67, and 75. After the Week 53 visit, background medications may be changed as deemed necessary by the investigator.

As part of the study, selected sites will take part in a substudy using HRCT scanning to measure potential airway wall structural changes including airway wall thickness. Sites will be selected on their ability and willingness to carry out the scans. Participation in this substudy is optional for subjects at the selected sites. An adequate number of sites will be identified in order to target recruitment of approximately 40 subjects into each of the 2 treatment groups for the HRCT substudy.

[figure not shown]

Figure 2.1-1 Study Flow Diagram

Q2W = every 2 weeks; Q4W = every 4 weeks; Wks = Weeks

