3.5 Summaries to Support the Primary Objective

The primary objective of this study is to evaluate the effect of two SC treatment regimens of 300 mg tralokinumab compared with combined placebo by assessing the asthma exacerbation rate over 52 weeks in adults with uncontrolled, severe asthma requiring high-dose ICS and LABA with or without additional controller medications. An asthma exacerbation is defined as a progressive increase of asthma symptoms (cough, wheeze, chest tightness, and/or shortness of breath) that does not resolve after the initiation of rescue medications and remains troublesome for the subject resulting in either 1) use of systemic corticosteroids (tablets, suspension or injection) or increase of a stable systemic maintenance dose for a duration of at least 3 consecutive days as prescribed or administered by the investigator or

healthcare provider; or 2) subject initiation of systemic corticosteroids for a duration of at least 3 consecutive days as outlined in the Asthma Action Plan provided to the subject by the investigator on Day 1 An asthma exacerbation event will be considered resolved 7 days after the last dose of OCS is administered (10 days after administration of an injectable corticosteroid). Courses of corticosteroids initiated after this time period would be considered a separate new asthma exacerbation.

Asthma exacerbation severity will be classified as follows:

- Moderate: Worsening symptoms requiring systemic corticosteroids for at least 3 consecutive days.
- Severe: Worsening symptoms requiring systemic corticosteroids and requiring urgent care evaluation and/or hospital admission.

Please note that a single depo-injectable dose of corticosteroid will be considered the equivalent to a 3-day course of systemic corticosteroids

The primary endpoint will be the annual rate of asthma exacerbations experienced by subjects after their first dose of investigational product up to their week 53 / Early Discontinuation visit.

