The crude asthma exacerbation rate will be estimated as a weighted mean (total number of exacerbations for the treatment group divided by the total duration of person follow-up) per the joint guidelines recommended by the ATS/ERS. The primary endpoint analysis will be conducted based on the ITT population using a Poisson regression model adjusted for overdispersion (Pearson Chi-Square correction) with treatment group, age, gender (male vs female), number of asthma exacerbations in the past year ($2 \text{ vs} > 2 \text{ but} \le 6 \text{ exacerbations}$), atopic asthma status (atopic vs. non-atopic), chronic OCS use (presence versus absence), and geographical region (United States/Canada/Western Europe, Eastern Europe, Asia, rest of world) as covariates and the log of number of days in the study as offset. Exacerbation rates, 85% CIs, rate ratios, 2-sided p-values will be provided based on the Poisson regression model. The primary endpoint will also be analyzed using a negative binomial regression model to assess the robustness with regard to the distributional assumptions. Pairwise comparisons between individual tralokinumab treatment group and combined placebo from Cohorts 1 and 2 will be conducted. Comparison between tralokinumab and placebo from the same cohort will be conducted as secondary analyses. Analysis based on the PP population will be performed as a sensitivity analysis.

The primary endpoint will also be analyzed using Cochran-Mantel-Haenszel row Mean Score Test. For analyses based on ITT Population, the adjusted number of exacerbations for subjects who withdraw from the study will be calculated using the following equation: [recorded number of exacerbations] / [number of days in the study] × 365.25.

Severe asthma exacerbations are of interest. The Analyses mentioned above will be conducted specifically for severe asthma exacerbations as well.

In addition, asthma exacerbations and severe asthma exacerbations between week 53 and end of the study, and asthma exacerbations and severe asthma exacerbations through the end of the study will also be summarized. Time to first exacerbation and time to first severe exacerbation will be analyzed as a supportive efficacy analysis to the primary objective. A Cox proportional hazard model will be fitted to data.

The number and proportion of subjects with different number of asthma exacerbations and severe asthma exacerbations (0, 1, 2, 3, and > 3) will be summarized by treatment group.

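### Section 3.5: three counting rules (event end under maintenance OCS, the person-time denominator, annualised CMH scores) can give wrong results if applied literally

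*SAP*

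**What the plan says.** **Event definition and closure (SAP 3.5).** A qualifying exacerbation includes an "increase of a stable systemic maintenance dose for a duration of at least 3 consecutive days". On closure the section says: "An asthma exacerbation event will be considered resolved 7 days after the last dose of OCS is administered", with a separate 10-day interval for injectables. It continues: "Courses of corticosteroids initiated after this time period would be considered a separate new asthma exacerbation". Section 2.1 lists OCS among the permitted additional controllers and keeps subjects on background therapy "with or without additional asthma controller medications at a stable dose during the treatment period and through Week 53". Randomisation is stratified "by chronic OCS use (presence versus absence"; the same factor is a covariate in the primary model and a subgroup.

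**Windows (SAP 3.5).** The primary endpoint counts events "after their first dose of investigational product up to their week 53 / Early Discontinuation visit". The Poisson model uses "the log of number of days in the study as offset". The crude rate uses person follow-up. Neither denominator is defined. Section 2.1 has follow-up visits to Week 75, and Section 3.5 itself places the end of the study after Week 53.

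**CMH mean-score test (SAP 3.5).** For subjects who withdraw, the count is rescaled as "recorded number of exacerbations] / [number of days in the study", multiplied by 365.25. The score type and a minimum follow-up are not stated.

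**The concern.** These sentences fix the numerator and denominator of the primary endpoint, so a programmer should be able to follow them without guessing.

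- (a) The definition admits events in maintenance-OCS subjects, but the closing rule refers to a dose that they do not reach in the counting window. If second and later orally treated events are lost, more are lost where the rate is higher, so the ratio is pulled toward 1 in a pre-specified stratum.
- (b) A denominator longer than the counting window lowers the reported annual rates, and weights completers and withdrawals differently.
- (c) Dividing one subject's count by a very short follow-up gives an extreme score. The plan avoids this for the crude rate by dividing total events by total follow-up.

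**Working it through.** **The plan's own figure.** Inputs from SAP 2.3: placebo rate 1.2 per year, 40% reduction (active rate 0.72), 80% power, alpha 0.1 (two-sided in Table 1). n = (1.645 + 0.842)² × (1/1.2 + 1/0.72) / (ln 0.60)² = 52.65, so 53 per arm, as stated. With overdispersion 1.2 the formula gives 63.2, so 64 against the stated 65. These inputs are used below; the figures themselves are not in dispute.

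**(a) Closure rule, literal reading.** With at most one countable event, the expected yearly count per subject is 1 − exp(−rate).

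| Placebo rate | Placebo count | Active count (true ratio 0.60) | Observed ratio | Placebo events lost |
|---|---|---|---|---|
| 1.2 (planned) | 0.699 | 0.513 | 0.734 | 42% |
| 0.5 (assumed lower rate) | 0.393 | 0.259 | 0.659 | 21% |

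The SAP gives no OCS share, so call it f. At the planned rate the overall ratio is [(1 − f) × 0.72 + f × 0.513] / [(1 − f) × 1.2 + f × 0.699].

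| Assumed f | 5% | 10% | 20% | 30% |
|---|---|---|---|---|
| Overall ratio | 0.604 | 0.608 | 0.617 | 0.627 |

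**(b) Denominator.** The counting window is 52 weeks = 364 days. Day 1 to Week 75 is 74 weeks = 518 days. 364/518 = 0.703, so a rate of 1.2 would be reported as 0.84, about 30% too low.

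For the ratio, assume that dropouts leave at mid-window (182 days) and all others are followed to 518 days. With dropout proportion q, the reported rate is the true rate × 364 × (1 − q/2) / [518(1 − q) + 182q].

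- q = 20%: factor 364 × 0.90 / 450.8 = 0.727.
- q = 10%: factor 364 × 0.95 / 484.4 = 0.714.
- 20% placebo against 10% active: 0.714/0.727 = 0.98, so a ratio of 1.00 reads 0.98 and 0.60 reads 0.589.
- 10% placebo against 20% active: 0.60 reads 0.611.
- Equal dropout: no change.

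**(c) Annualised scores.** One event and withdrawal at day 14 scores 365.25/14 = 26.1. In an arm of 130 this adds 26.1/130 = 0.20 to the mean score. The effect on the test was simulated with 130 per arm, Poisson counts and two-sided 0.15, with and without one such subject in the active arm.

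| Rates (placebo, active) | Scores | Power without | Power with |
|---|---|---|---|
| 0.5, 0.3 | raw | 86% | 0% |
| 0.5, 0.3 | rank | 84% | 81% |
| 1.2, 0.72 | raw | 99% | 34% |
| 1.2, 0.72 | rank | 99% | 99% |

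Simulated values carry an error of about one point.

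**The case against.** **On (a),** a reader might infer that exacerbations in maintenance-OCS subjects never resolve. The SAP does not establish that. The sentence after the closure rule speaks of courses, so the last dose can be read as that of the treating course, and injectable-treated events have their own interval. The definition names maintenance-dose increases, so the authors had these subjects in mind. This makes the literal outcome less likely. It does not supply the missing rule for how an event treated by a dose increase ends. The 0.73 also applies to one stratum at the planned rate of 1.2, and Section 2.3 reports that blinded estimates run below that.

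**On (b),** a reader might infer that the offset is set to Week 75. It is not: the term is undefined, the primary table is titled as running through Week 53, and a separate programming plan, not at hand, may settle it. At Stage 1 not every subject will have reached Week 75, so 30% is an upper bound, and the SAP gives no accrual period from which to narrow it. Still, Section 3.5 tabulates rates over three windows, which one undefined phrase cannot serve, and Section 3.1 repeats the primary-endpoint analyses at the end of the study.

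**On (c),** the test is supportive. The primary Poisson model and the negative binomial robustness model do not annualise per subject. Rank scores are not excluded, the day-14 case is hypothetical, and under no effect at a rate of 0.5 one such subject lowered simulated rejection (9% against 15%). The loss of power under a true effect with raw scores stands.

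**Conclusion.** The three rules should be tightened, as wording that can misfire and not as a demonstrated error in the primary analysis.

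- (a) is a real mismatch between the event definition and the closure sentence. Its literal effect is sizeable in the maintenance-OCS stratum (0.60 to 0.73 at placebo rate 1.2) and small overall (0.604 to 0.627). The overall figures rest on an assumed 5 to 30% OCS share and on at most one event counted per subject.
- (b) bears mainly on absolute rates, by up to 30% if the denominator ran from Day 1 to Week 75. The shift of about 0.01 to 0.02 in the ratio rests on an assumed 10-point imbalance in mid-window dropout.
- (c) can decide a supportive test if raw scores are used. It leaves the primary model untouched.

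The documents do not support the stronger inference that the primary comparison is compromised.

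**What to change.** Amend Section 3.5 and the programming specification, before unblinding.

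- (a) Reconcile the event definition with the resolution sentence. For event counting only, the end of an event in maintenance-OCS subjects should refer to the course or dose increase that treated it. No change to treatment is implied.
- (b) Replace study days in the offset and the annualisation by days from first dose to the earlier of the Week 53 and Early Discontinuation visits (or the data cut). Use the same person-time for the crude rate, and give the matching window for each of the other tabulated periods.
- (c) Specify rank (modified ridit) scores for the CMH test. The price is slightly lower power when there are no early withdrawals (84% against 86% at rates 0.5 and 0.3).

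The cost is a few sentences; no new data are needed and no stated sample-size figure changes.

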2.2 Randomization and Blinding

2.2.1 Subject Randomization Procedures and Treatment Allocation

An IXRS will be used for randomization to a cohort and assignment of blinded investigational product kit numbers. A subject is considered randomized into the study when the investigator or designee notifies the IXRS that the subject meets eligibility criteria and the IXRS provides the assignment of blinded investigational product kit numbers to the subject.

Subjects will be randomized in a 1:1 ratio to one of 2 cohorts. Within each cohort, subjects will be randomized in a ratio of 2:1 to receive SC tralokinumab (300 mg) or placebo. Subjects will be stratified at screening by the number of asthma exacerbations in the past year (2 versus > 2 but \leq 6 exacerbations) and by chronic OCS use (presence versus absence). To maximize the probability of obtaining treatment balance within Japanese population for the purpose of PMDA filing, the Japanese will be randomized separately.

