The accrual of asthma exacerbations is monitored during the study and blinded estimates of the annual asthma exacerbation rate in the placebo group are calculated. These estimates are consistently lower than the planned placebo rate of 1.2 exacerbations per year. In order to maintain adequate power to detect a 40% reduction in the annual asthma exacerbation rate for each tralokinumab cohort compared to placebo, the significance level for the data analysis will be raised from two-sided 0.1 to two-sided 0.15.

Sites in Japan will randomize approximately 65 Japanese subjects as part of the overall sample size. In the event that enrollment of the Japanese subjects is significantly delayed, and to ensure a timely Stage 1 analysis, non-Japanese sites may contribute sufficient subjects to reach the sample size required for the Stage 1 analysis (at least 390 subjects). In this event, sites in Japan will be permitted to continue enrollment until such time as approximately 65 Japanese subjects have been enrolled.

3 Statistical Methods

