3.1 General Considerations

Two formal analyses (Stage 1 analysis and Stage 2 analysis) as well as an interim analysis are planned for the study.

The Stage 1 analysis for the overall population will be conducted after the last non-Japanese subject has completed the Week 53 visit or discontinued prematurely (this analysis will include all Japanese subjects who have completed Week 53). The Stage 2 analysis for long-term safety follow-up will be performed after all subjects have completed the study or discontinued prematurely. During the Stage 1 analysis, all the efficacy and safety data

Version 2.0

collected will be analyzed. Pairwise comparisons between individual tralokinumab treatment groups and combined placebo will be conducted. The primary analysis for which the study is powered will be completed in the Stage 1 analysis, and the analyses based on primary efficacy endpoint will be repeated for overall population (which includes all subjects enrolled into the study) at the end of the study as sensitivity analysis.

The interim analysis will be conducted after the last non-Japanese subject randomized into the study has completed the Week 39 visit or discontinued prematurely. All data available will be analyzed as part of the interim analysis. The details of the interim analysis will be specified in unblinding plan for interim analysis.

The overall type I error rate (two-sided) will be controlled at the 0.15 level using O'Brien-Fleming alpha spending function based on the actual person-years follow-up observed. For example, if the information fraction at the interim analysis is 88%, then the two-sided type I error rate will be 0.105 for the interim analysis and 0.128 for final analysis, respectively. The interim analysis will have minimal impact on the power of the study at the final analysis, which is estimated to be approximately 78%.

Three sets of analyses will be performed at Stage 1. They are: 1) analyses based on overall population; 2) analyses for Japan only subjects (n=45); and 3) analyses for non-Japanese subjects. The go/no-go decision will be based on stage 1 analysis for overall population.

In addition, for PMDA consultation, the same analyses for all Japan subjects (n=64) will be conducted when all Japan subjects complete week 53 follow-up or discontinue prematurely.

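### The primary model reflects the separate randomisation of Japanese subjects only through an undefined Asia level; making Japan its own region level is a free, small improvement

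*SAP*

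**What the plan says.** Section 2.2.1 (and Section 2.1 in the same terms) names two stratification factors: "Subjects will be stratified at screening by the number of asthma exacerbations in the past year", in two categories, "and by chronic OCS use (presence versus absence". It then adds a further restriction: "To maximize the probability of obtaining treatment balance within Japanese population for the purpose of PMDA filing, the Japanese will be randomized separately".

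Section 2.3 gives the size of that group: "Sites in Japan will randomize approximately 65 Japanese subjects as part of the overall sample size". It also lets Japanese sites go on enrolling after the other sites have filled the sample. Section 3.1 plans, beside the overall Stage 1 analysis, "analyses for Japan only subjects (n=45") and "analyses for non-Japanese subjects", and later an analysis of all 64 Japanese subjects.

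Section 3.5 specifies the primary analysis as a "Poisson regression model adjusted for overdispersion (Pearson Chi-Square correction"), with treatment, age, gender, past-year exacerbations, atopic status, chronic OCS use and "geographical region (United States/Canada/Western Europe, Eastern Europe, Asia, rest of world) as covariates". There is no Japan term. Section 3.6.2 lists geographical region among the potential covariates of an optional spirometry ANCOVA, without giving its levels.

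**The concern.** A separate randomisation list works as a stratum whether or not the plan calls it one. Treatment is balanced within Japanese and within non-Japanese subjects, and a model that follows the design would carry that split. The SAP does this for its two named factors, with the categories used at randomisation. For the Japanese layer it has only the Asia level, and the reader cannot tell whether that level is the same group.

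If Asia is wider than Japan, the part of the Japan effect that the Asia level misses stays in the residual. The Pearson correction reads it as overdispersion and widens the intervals for both regimens. What is at stake is a little precision, in a trial that has already raised its significance level to two-sided 0.15 because exacerbations were fewer than planned (Section 2.3). There is also a point of pre-specification: if the country grouping of a primary-model covariate is not written down, it could be settled after results are known.

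**Working it through.** **1. Randomisation against model.**

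| Randomisation layer | Term in the Section 3.5 model | Match |
|---|---|---|
| Past-year exacerbations, 2 vs more than 2 up to 6 | Same two categories | Yes |
| Chronic OCS use, yes/no | Same two categories | Yes |
| Japanese vs non-Japanese | Asia, one of four region levels | Only if Asia is Japan alone |

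**2. Planning figure.** No figure in the SAP is disputed, but the planning basis can be reproduced. With rates 1.2 and 0.72 per year (a 40% reduction), 80% power and two-sided alpha 0.1:

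n per arm = (1.645 + 0.842)² × (1/1.2 + 1/0.72) / (ln 0.6)² = 52.65, so 53 as stated. Multiplying by the overdispersion of 1.2 gives 53 × 1.2 = 63.6, so 64 against the stated 65. The point below changes none of this.

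**3. Effect on the standard error.** Assumed, not in the SAP: 390 subjects, 45 of them Japanese (the Stage 1 figure in Section 3.1) and 45 other Asian; placebo rate 0.9 per year; rate ratio 0.6; gamma heterogeneity 0.3; 1:1:1 allocation done separately in Japanese and non-Japanese subjects; 600 simulated trials per scenario.

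| Japanese rate relative to the others | SE of log rate ratio, Asia term only | SE with a Japan term | Reduction |
|---|---|---|---|
| one third | 0.174 | 0.171 | 0.003/0.174 = 1.7% |
| one half | 0.172 | 0.171 | 0.001/0.172 = 0.6% |
| twofold | 0.162 | 0.160 | 0.002/0.162 = 1.2% |
| threefold | 0.158 | 0.152 | 0.006/0.158 = 3.8% |

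In the most extreme row, the 85% CI around a rate ratio of 0.6 is exp(ln 0.6 ± 1.44 × 0.158) = 0.478 to 0.753 with the Asia term, and exp(ln 0.6 ± 1.44 × 0.152) = 0.482 to 0.747 with the Japan term.

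**4. Effect on the test.** A separate simulation used 390 subjects in three equal arms, 45 or 65 Japanese subjects in their own permuted blocks of 6, two-sided alpha 0.15 and 2,000 runs per setting. Assumed, not in the SAP: control rate 0.9, frailty variance 0.2, the block size, 0, 30 or 60 other-Asian subjects, and a Japanese rate 0.4, 1 or 2 times the rest.

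- No other-Asian subjects: the two models are identical.
- 30 or 60 other-Asian subjects: power differs by at most 0.4 points (94.0% with Asia, 94.4% with Japan split out) and the mean rate ratio by at most 0.001.
- Type I error differs by about 1 point at most. Where the gap is visible, the Asia model is the lower: 0.134 vs 0.1435 and 0.149 vs 0.1585. The simulation error of one such rate is √(0.15 × 0.85/2000) = 0.008. Both models were fitted to the same data, so their difference is known somewhat better than that, but the gaps remain small.

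Both simulations give other-Asian subjects the same baseline rate as the rest of the trial. What matters is the contrast between Japan and other Asia; if the two share a rate, the split gains nothing.

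**The case against.** The strongest reply is that the mismatch may not exist. The SAP speaks of about 100 sites worldwide, of sites in Japan and of non-Japanese sites, and nowhere of an Asian site outside Japan. A reader might infer from the word Asia that Japan is pooled with other countries; the document does not say so. If Japan is the only Asian country, the Asia level is the Japanese layer. This stands, and the point is conditional for that reason.

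A reader might also say that the SAP drops one of three stratification factors. It names only two, and both are in the model. The separate randomisation has a stated regulatory purpose, which the planned Japan analyses serve. Those are subset analyses, and they do not oblige the overall model to carry a Japan term. This too stands, although a separate list still restricts the allocation whatever its purpose.

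Two further inferences fail. The primary analysis is not biased or invalid: treatment is randomised within both groups, a rate ratio from a log-link model is not shifted by leaving out a balanced covariate, and any error in the intervals is on the conservative side. Nor does Section 3.6.2 fix the same grouping, since region is only a potential covariate there and has no levels.

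What is left is plain from the text: there is no explicit Japan term, and a covariate of the primary model has a level whose membership is not defined.

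**Conclusion.** The point holds as a low-priority improvement that costs almost nothing. It is not an error that threatens the primary analysis. If Asia includes countries other than Japan, the model follows the Japanese randomisation only in part, and standard errors and 85% CIs are slightly conservative: 0 to about 4% of the standard error, and at most 0.4 points of power. If Asia is Japan only, the numerical effect is nil and only the label needs clarifying. These sizes rest on assumed rates, heterogeneity and numbers of other-Asian subjects, none of which the SAP gives. Neither simulation included the remaining covariates of the primary model or the interim alpha spending.

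**What to change.** Before unblinding, and so before the interim analysis, redefine region in Section 3.5 as United States/Canada/Western Europe, Eastern Europe, Japan, other Asia, and rest of world. Take Japan from the separate randomisation list, so that the level matches the allocation exactly. List the countries in each level. If other Asia is sparse, put it in rest of world and not with Japan. Use the same definition wherever region is a covariate, including the ANCOVA in Section 3.6.2 if it is run.

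The cost is one line of text. Five levels use one more degree of freedom than the present four; merging other Asia into rest of world uses none. If no other Asian country takes part, the change is a relabelling and no result moves.
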